6.2 Implant/Procedure/Post-Procedure

Refer to the IFU for procedural and post-procedural instructions.

6.3 Attempt to treat

Subjects who are consented, in whom vascular access for the AMPLATZER LAA Occluder was initiated, but the device was not implanted, will be considered “Attempt to Treat”. The subject will be followed for 7 days or until discharge, whichever is later. Retrospectively enrolled subjects will include “Attempt to Treat” subjects; AEs that occurred within 7 days following the implant attempt or by discharge, whichever was later, will be captured.

6.4 Scheduled Follow-ups

Required follow-up visits for subjects who are prospectively implanted with an AMPLATZER LAA Occluder will be at 2 months, followed by a 6-month telephone follow-up, and 12 and 24-month follow-up visits. For retrospective subjects, follow-up visits after enrollment will be conducted per protocol, and will be based on the date of implant. However, all AEs from the time of the implant procedure will be collected. Refer to **Table 2** for required follow-up testing and assessments. Subjects in whom vascular access is initiated for an AMPLATZER LAA Occluder, but the device is not implanted, will be considered “Attempt to Treat” and will be followed for 7 days until discharge, whichever is later.

6.5 Unscheduled Visits

If an unscheduled visit occurs, a Follow-up eCRF should be completed to capture data collected at the visit as well as pertinent additional eCRFs (medication, echo, and adverse event assessments as applicable).

In the event of a confirmed stroke, a TOE is required as soon as possible, but no later than 7 days after the stroke. The Stroke/TIA assessment, modified Rankin Scale, and Echo eCRFs should be completed and applicable imaging submitted to the Sponsor. Ninety (90) days after the event, the Stroke/TIA assessment and mRS should be repeated and applicable eCRFs submitted to the sponsor.

6.6 Sponsor Representatives

Trained Sponsor personnel may perform certain study activities to ensure compliance to the clinical protocol and may provide technical expertise. Monitoring may be performed by Abbott and/or authorized designees according to the International Organization for Standardization (ISO) 14155 for post market studies, and applicable Abbott standard operating procedures and work instructions. Qualified monitors will ensure investigators comply with this clinical protocol and ISO 14155 post market requirements.

Sponsor representatives will periodically request source documents, resolution of discrepancies, submission of echocardiography imaging etc. for data cleaning and reporting purposes.

6.7 Subject Study Completion

Subjects will complete their participation in the study at the 2-year follow-up visits and will return to receiving medical care per their physician’s recommendations.

6.8 Subject Withdrawal

Subjects must be informed about their right to withdraw from the study at any time and for any reason without sanction, penalty, or loss of benefits to which the subject is otherwise entitled. Withdrawal from the study will not jeopardize their future medical care or relationship with the

investigator. Subjects will be asked to specify the reason for their termination, but have the right not to answer.

All reasonable efforts should be made to retain the subject in the study until completion of the study.

Reasons for subject withdrawal include, but are not limited to:

- Subject withdraws consent
- Subject dies (adverse events leading to death must be documented on an Adverse Event eCRF)
- Subject did not have a successful implant and does not have a study device implanted (subjects who had an unsuccessful implant, the withdrawal date should be at 7 days post-implant attempt)
- Subject is 'lost to follow up' (a subject will be considered "lost to follow-up" after a minimum of 2 attempted phone calls and a letter to the subject from study site personnel. Attempts to contact subject must be documented in the subject's study chart and/or medical record. If phone attempts are unsuccessful, a letter should be sent to the subjects last known address)

If a subject withdraws from the study, the site will record the subject's reasons for withdrawal on the Withdrawal eCRF.

7. Compliance Statements

The study will be performed in accordance with the most current versions of the World Medical Association (WMA) Declaration of Helsinki (**Appendix C**), ISO 14155, and any regional and/or national regulations and will be compliant to these International Standards and any regional and national regulations, as appropriate.

The investigator will not enroll subjects or obtain informed consent from any subject prior to obtaining EC approval and authorization from the Sponsor in writing for the study. For prospective enrollments, the subject must sign the study informed consent form prior to implant procedure.

If additional requirements are imposed by the EC, those requirements will be followed, if appropriate. If any action is taken by an EC, and regulatory requirements with respect to the study, that information will be forwarded to the Sponsor.

As the Sponsor, Abbott has taken general liability insurance in accordance with the requirements of applicable local laws. Appropriate Abbott country representatives will be utilized to interpret the requirements regarding the type of insurance that will be provided to subjects, and such information will be incorporated into the informed consent form, as applicable. If required, additional subject coverage or study specific insurance may also be provided by the Sponsor.

8. Serious Adverse Events, Serious Adverse Device Effects, Deaths and Device Deficiencies

Only serious adverse events (SAEs) will be collected for this study. Serious adverse events are classified as serious adverse events or serious adverse device effects (SADEs). A planned hospitalization for a pre-existing condition is not considered a serious adverse event.

8.1 Serious Adverse Events

A serious adverse event is an adverse event that led to:

- Death
- A serious deterioration in the health of the subject, that either resulted in:

- A life-threatening illness or injury OR
- A permanent impairment to a body structure or a body function OR
- An in-patient or prolonged hospitalization OR
- A medical or surgical intervention to prevent life-threatening illness or injury or permanent impairment to a body structure or a body OR
- A malignant tumor OR
- Fetal distress, fetal death or a congenital abnormality or birth defect

8.1.1 Serious Adverse Device Effect

A serious adverse device effect is a serious adverse event related to the device or procedure which resulted in any of the consequences characteristic of a serious adverse event, or that might have led to any of these consequences if suitable action had not been taken or intervention had not been made or if circumstances had been less opportune.

8.1.2 Assessing, recording and reporting serious adverse events, serious adverse device effects, and device deficiencies/complaints

Safety surveillance within this study and the safety reporting performed both by the investigator and Sponsor starts as soon as vascular access has been initiated. The safety surveillance and the safety reporting will continue until the last visit has been performed, the subject is deceased, or the subject withdraws from the study.

All serious adverse events (including deaths), serious adverse device effects, and device deficiency information (if applicable) will be collected throughout the clinical study and reported to the Sponsor. Investigators will record all serious adverse events, serious adverse device effects, and deaths on the appropriate eCRF. Device deficiencies/complaints will be reported per country reporting timeline requirements using the standard process per country regulations.

For any serious adverse event (including deaths) and any serious adverse device effect, the investigator shall notify the Sponsor within 3 calendar days of the investigator's awareness of the event and provide the Sponsor with all necessary documentation needed.

Records relating to the subject's subsequent medical course must be maintained and submitted (as applicable) to the Sponsor until the event has subsided or, in case of permanent impairment, until the event stabilizes and the overall clinical outcome has been ascertained. Additional information may be requested, when required, by the Sponsor in order to support the reporting of serious adverse events to the CEC, regulatory authorities and/or other authorities.

Serious adverse events and serious adverse device effects should be monitored by the investigator until resolved. The status of the subject's condition should be documented at each follow-up visit.

Events reportable to the Sponsor, EC, CAs and regulatory authorities (as applicable) include:

- All serious adverse device effects
- All serious adverse events (including deaths and whether or not the event is considered device or procedure related)

The Sponsor will ensure that all events and device deficiencies are reported to the relevant authorities per country specific regulations.

8.1.3 Subject death

All subject deaths with all necessary documentation needed are to be reported to the Sponsor within 3 calendar days upon the investigator's awareness of the event. The Sponsor must report the death (classified as a serious adverse event) to the National Competent Authorities (NCAs) where the study has commenced no later than 2 calendar days after awareness of the event. An Adverse Event eCRF should be completed and include additional detail surrounding the death and cause of death. The principal investigator should also record observed device deficiencies and assessment, if applicable.

8.2 Device Deficiency/Complaint Handling

During the trial, the investigator will be responsible for reporting all device deficiencies per country reporting timeline requirements. A device deficiency is defined as an inadequacy of a medical device with respect to its identity, quality, durability, reliability, safety or performance and includes malfunctions, and inadequate labeling.

Abbott will manage all device deficiencies related to the identity, quality, durability, reliability, safety or performance of the marketed study device and reporting to the appropriate regulatory bodies.

9. Data Management

Overall, the Sponsor will be responsible for data handling. The Sponsor and/or its affiliates will be responsible for compiling and submitting all required reports to governmental agencies.

Data will be analyzed by the Sponsor and may be transferred to the Sponsor's locations outside of Canada, Europe and/or any other worldwide regulatory authority in support of a market-approval application.

Abbott respects and protects personally identifiable information that is collected or maintained. As part of its commitment, Abbott is certified to the U.S. - European Union Framework and PIPEDA-Canada privacy act. Agreements regarding human resources and subject clinical trial personal information. The privacy of each subject and confidentiality of his/her information will be preserved in reports and when publishing any data. Confidentiality of data will be observed by all parties involved at all times throughout the clinical study. All data will be secured against unauthorized access.

Electronic CRFs will be used in this study, as noted below and in the data management plan. Informed consent documents will be translated to each country's language, as applicable. If additional documentation is required for any reason (e.g. procedural notes for an adverse event), it is to be appropriately redacted/de-identified prior to being sent to Abbott. Source documents will be collected and translated, as needed, for CEC meetings, reporting, etc.

The principal investigator or institution will provide direct access to source data during and after the clinical study for monitoring, audits, EC review and regulatory authority inspections.

9.1 Data Management Plan

A detailed data management plan (DMP) will be established to ensure consistency of the collected data. This document will include procedures used for data review, database cleaning, and issuing and resolving data queries. If appropriate, the DMP may be updated throughout the study duration. All revisions will be tracked and document controlled.

Electronic CRF data will be captured in a validated electronic database management Oracle Clinical system hosted by Abbott. Only authorized site personnel will be permitted to enter the data through the electronic data capture (EDC) system deployed by Abbott. An electronic audit trail will be used to track any subsequent changes of the entered data.

9.2 Document and Data Control

9.2.1 Document and data traceability

The investigator will ensure accuracy, completeness, legibility and timeliness of the data reported to the Sponsor on the eCRFs and in all required reports.

9.2.2 Recording data

Source documents will be created and maintained by the investigational site throughout the duration of the clinical study. Data reported on the eCRFs will be derived from, and be consistent with, these source documents, and any discrepancies will be explained in writing.

The eCRFs will be signed and dated (validated eCRF) by the authorized site personnel, as specified in the Data Management Plan.

10. Risks and Benefits

10.1 Anticipated Clinical Benefits

Patients suitable to receive the AMPLATZER LAA Occluder should be deemed by their physician to have an appropriate rationale to seek an alternative to pharmacologic therapy such as the inability to tolerate long term anticoagulants. The AMPLATZER LAA Occluder is intended to be an alternative long term stroke prophylaxis when long term anticoagulation therapy is unacceptable. The potential benefit of participating in this clinical study are close follow-up of the subject by their treating physicians.

10.2 Anticipated Adverse Events and Adverse Device Effects

Anticipated adverse events and adverse device effects may occur during and after the AMPLATZER LAA Occluder implant procedure. Serious adverse event definitions are provided in **Section 8**. Refer to IFU for a complete list of potential anticipated serious adverse events.

10.3 Risks

The risks associated with the AMPLATZER LAA Occluder are no different from the risks associated with undergoing implant of an LAA Occluder with other commercially available transcatheter devices.

10.4 Risk to Benefit Rationale

Risks associated with participating in this clinical study are no different from risks associated with undergoing LAAO implant with a commercially available transcatheter device. A potential benefit of participation in this clinical study may be close follow-up of the subject by their treating physicians.

10.5 Residual Risks Associated with the Device

The AMPLATZER Left Atrial Appendage Occluder device is market approved in all the countries where the study will be conducted. The risk profile of the LAA Occluder device implant procedure is described in the IFU, and **Section 8** of this protocol. Risks associated with participating in this clinical study are no different from risks associated with undergoing LAAO implant with a commercially available transcatheter device.

10.6 Steps to Control or Mitigate Risks

The Sponsor will select investigators qualified by training and experience to participate in this study. Participating sites will be selected based upon qualifications of the principal investigator. During the study, sites may be subject to quality assurance audits by the Sponsor (or designee), as well as monitoring visits to assess data integrity and study compliance. Any additional risk is mitigated with vigilance reporting for a licensed product.

11. Clinical Events Committee (CEC)

A CEC will be responsible for providing an independent adjudication of study endpoints as outlined in the CEC Charter.

12. Monitoring

It is the responsibility of Abbott as the Sponsor of the study to ensure the study is conducted, recorded, and reported according to the approved protocol, subsequent amendment(s), applicable regulations, and guidance documents. Monitoring will be conducted according to the study-specific monitoring plan.

Prior to beginning the clinical investigation, the Sponsor will contact the investigator or designee to discuss the clinical investigation and data requirements. A designated monitor will periodically review the subject records and associated source documents. The investigator shall make subject and study records available to the clinical monitor for monitoring.

Additionally, centralized monitoring may occur through routine internal data review. This monitoring is designed to identify missing and inconsistent data, data outliers, and potential protocol deviations that may be indicative of site non-compliance.

13. Regulatory Inspections

The investigator and/or delegate should contact SJM as soon as possible upon notification of a governmental agency inspection at the site. A clinical monitor or designee will assist the investigator and/or delegate in preparing for the audit.

An investigator, or any person acting on behalf of such a person with respect to the study, will permit authorized governmental agency employees, at reasonable times and in reasonable manner, to inspect and copy all records relating to the study.

An investigator will permit authorized governmental agency employees to inspect and copy records that identify subjects, upon notice that governmental agency has reason to suspect that adequate informed consent was not obtained, or that reports required to be submitted by the investigator, to the Sponsor or EC have not been submitted or are incomplete, inaccurate, false or misleading.

14. Statistical Methods

14.1 Primary Endpoints

There are three primary endpoints, two effectiveness endpoints and one safety endpoint.

14.1.1 Primary Effectiveness Endpoint 1:

Primary effectiveness endpoint 1 is the occurrence of the composite of stroke (including ischemic or hemorrhagic), systemic embolism, or cardiovascular or unexplained death at 24 months.

Hypothesis:

Ho: $\lambda_1 \geq 9.6\%$

Ha: $\lambda_1 < 9.6\%$,
where λ_1 is the rate of primary composite endpoint 1 at 24 months.

Analysis Methods:

Kaplan-Meier analysis will be used to estimate the event rate of at 24 months (731 days post implant). The 97.5% upper confidence bound for the event rate must be less than 9.6% in order to declare success. [REDACTED]

Analysis Population:

Subjects in this study who receive an implant of the AMPLATZER LAA Occluder will be included in the analysis.

14.1.2 Primary Effectiveness Endpoint 2:

Primary effectiveness endpoint 2 is the occurrence of the composite of ischemic stroke or systemic embolism at 24 months.

Hypothesis:

Ho: $\lambda_2 \geq 6.6\%$

Ha: $\lambda_2 < 6.6\%$,

where λ_2 is the rate of primary composite endpoint 2 at 24 months.

Analysis Methods:

Kaplan-Meier analysis will be used to estimate the rate of event at 24 months (731 days post implant). The 97.5% upper confidence bound for the event rate must be less than 6.6% in order to declare success. [REDACTED]

Analysis Population:

Subjects in this study who receive an implant of the AMPLATZER LAA Occluder will be included in the analysis.

14.1.3 Primary Safety Endpoint:

The primary safety endpoint is the occurrence of one of the following events between the time of implant and within 7 days of the procedure or by hospital discharge, whichever is later: All-cause death, ischemic stroke, systemic embolism, or device or procedure related events requiring open cardiac surgery or major endovascular repair (percutaneous catheter drainage of pericardial effusion, snaring of an embolized device, thrombin injection to treat femoral pseudoaneurysm, and nonsurgical treatments of access site complication will not be included in the assessment of the third primary endpoint).

Hypothesis:

Ho: $P \geq 2.66\%$

Ha: $P < 2.66\%$,

where P is the proportion of subjects experiencing a primary safety event within 7 days of the procedure or by hospital discharge, whichever is later.

Analysis Methods:

The proportion of subjects experiencing a primary safety endpoint will be estimated. The 97.5% upper confidence bound for the proportion of subjects experiencing a safety event will be calculated using the exact binomial method. The 97.5% upper confidence bound for the [REDACTED]

proportion must be less than 2.66% in order to declare success. [REDACTED]

Analysis Population:

Subjects who undergo an implant attempt with the AMPLATZER LAA Occluder will be included. An attempt is defined as a subject in whom vascular access has been initiated.

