4.2.3 Enrollment period and study duration

4.3 Endpoints

4.3.1 Primary endpoints

This study has three primary endpoints:

1. Efficacy Endpoint 1: The occurrence of the composite of stroke (including ischemic or hemorrhagic), systemic embolism and cardiovascular or unexplained death at 24 months
2. Efficacy Endpoint 2: The occurrence of ischemic stroke or systemic embolism at 24 months
3. Safety Endpoint: The occurrence of one of the following events between the time of implant and within 7 days of the procedure or by hospital discharge, whichever is later: all cause death, ischemic stroke, systemic embolism, or device or procedure-related events requiring open cardiac surgery or major endovascular repair*

* NOTE: Percutaneous catheter drainage of pericardial effusion, snaring of an embolized device, thrombin injection to treat femoral pseudoaneurysm and nonsurgical treatments of access site complications will not be included in the assessment of the third primary endpoint.

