The study is a post-approval study to compile real world outcome data on the use of the Amplatzer Cardiac Plug (“ACP”) and the next generation Amplatzer Amulet left atrial appendage occluder (“Amulet”) upon its approval by Health Canada, in subjects with non-valvular atrial fibrillation who are at increased risk for stroke and systemic embolism. [REDACTED]

1.3 **Clinical Investigation Design**

The Amplatzer family of left atrial appendage (“LAA”) occluder devices (ACP and Amulet) will be clinically evaluated through this post-approval study. This is a prospective, multicenter, non-randomized, observational, post-approval study on subjects who will undergo the implant of an Amplatzer LAA occluder.

1.4 **Endpoints**

As the coronavirus disease 2019 (COVID-19) has spread around the world, Abbott has taken steps to minimize the potential confounding effect of the disease. In alignment with the guidance documents “FDA Guidance on Conduct of Clinical Trials of Medical Products during the COVID-19 Public Health Emergency,” updated 03JUN2020, “Statistical Considerations for Clinical Trials During the COVID-19 Public Health Emergency,” dated June 2020, and EU “Guidance on the Management of Clinical Trials During the COVID-19 (Coronavirus) Pandemic,” updated 28APR2020, additional consideration was given to the impact of COVID-19 on the primary and secondary endpoint analysis. [REDACTED]

1.4.1 **Primary Safety Endpoint**

The primary safety endpoint is the occurrence of one of the following events between the time of implant and 7 days post-procedure or hospital discharge (whichever is later): all cause death, ischemic stroke, systemic embolism, or device- or procedure-related events requiring open cardiac surgery or major endovascular repair.

Percutaneous catheter drainage of pericardial effusion, snaring of an embolized device, thrombin injection to treat femoral pseudoaneurysm, and nonsurgical treatments of access site complications will not be included in the assessment of the primary safety endpoint.

1.4.2 **Primary Efficacy Endpoints**

Primary effectiveness endpoint 1 is the occurrence of stroke (including ischemic or hemorrhagic), systemic embolism, cardiovascular death, or unexplained death through 24 months.

Primary effectiveness endpoint 2 is the occurrence of ischemic stroke or systemic embolism through 24 months.

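### The primary safety window opens at implant, but the population tested is everyone with vascular access; read literally, this leaves pre-implant and failed-attempt events uncounted

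*Protocol*

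**What the plan says.** **Window.** Protocol 14.1.3 words the endpoint as "occurrence of one of the following events between the time of implant and within 7 days of the procedure or by hospital discharge"; the later of the two applies. The synopsis and Protocol 4.3.1 use the same start. SAP 1.4.1 agrees: "one of the following events between the time of implant and 7 days post-procedure or hospital discharge".

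**Population.** Protocol 14.1.3 analyses all subjects with an implant attempt: "An attempt is defined as a subject in whom vascular access has been initiated". SAP 2.3.1.1 uses the attempt population. Protocol 6.3 makes clear that attempts include subjects in whom access was started but no device was implanted.

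**Hypothesis.** The same section 14.1.3 continues: "where P is the proportion of subjects experiencing a primary safety event within 7 days of the procedure or by hospital discharge". This refers to the procedure and does not mention implant.

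**Data collection.** Under Protocol 8.1.2, safety surveillance "starts as soon as vascular access has been initiated"; Protocol 6.1 and SAP 3.2 say the same. Failed attempts are followed for 7 days or to discharge, whichever is later (6.3, 6.4). For retrospectively enrolled failed attempts, "AEs that occurred within 7 days following the implant attempt or by discharge, whichever was later, will be captured".

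**Decision rule.** The exact binomial 97.5% upper confidence bound must lie below 2.66%.

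**The concern.** The start of the window and the denominator do not match. An implanted subject who has a stroke, an embolism or a perforation needing surgery after access but before the device is placed has the event before the window opens. A subject whose implant is abandoned has no time of implant at all, so the definition gives no point at which that subject's window starts. Both subjects still count in the denominator.

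These are complications that a procedural safety endpoint exists to capture, and some of them are reasons for abandoning an implant. Under the literal wording, the same complication could count or not depending on whether a device was later released. The test is pass/fail on a primary endpoint, and an error of this kind can only lower the rate. The counting rule should therefore be fixed in advance and not left to adjudicators or programmers.

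**Working it through.** **Step 1. Does the visible text fix the start?** The definition uses two different words: implant for the opening of the window, procedure (or discharge) for its close. Elsewhere the protocol keeps implant and attempt apart. Section 6 collects retrospective events from the date of either one, and section 14.1 uses implanted subjects for effectiveness but attempted subjects for safety. The hypothesis line in 14.1.3 mentions only the procedure, but it counts a primary safety event, a term defined just above with the implant start. In the SAP, the proportion is of subjects with a primary safety endpoint event (2.3.1.1), which leads back to the implant start in 1.4.1. The visible text therefore supports two readings:

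- Literal reading: events before implant and all events in failed attempts are outside the window.
- Procedure reading: they are inside it, and there is no bias.

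**Step 2. The decision rule.** The visible text gives no expected safety rate, power or number of attempted subjects (SAP 2.4 is redacted), so there is no planned figure to reproduce. The rule itself can be rebuilt. For x events in n subjects, the exact bound is U(x, n) = the 0.975 quantile of Beta(x + 1, n − x), and success requires U < 2.66%.

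| n (assumed) | most events that pass | U | next count | U |
|---|---|---|---|---|
| 1000 | 16 | 2.585% | 17 | 2.708% |
| 500 | 6 | 2.593% | 7 | 2.863% |

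The 1000 is the overall size in Protocol 4.2.2, to which other post-approval studies also contribute; taking it as the number attempted is an assumption. The 500 is purely illustrative.

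**Step 3. Effect of uncounted events at n = 1000.** Let the true rate, counted from access, be 2.66% (26.6 expected events), and let a share f of events fall outside the literal window. The chance of declaring success is P(X ≤ 16), where X is binomial with n = 1000 and probability 0.0266 × (1 − f).

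| f (assumed) | events missed, 26.6 × f | counted rate | chance of success |
|---|---|---|---|
| 0 | 0 | 2.660% | 0.018 |
| 5% | 1.33 | 2.527% | 0.032 |
| 10% | 2.66 | 2.394% | 0.055 |
| 20% | 5.32 | 2.128% | 0.146 |

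The nominal one-sided level is 0.025. With every event counted the rule stays below it; with 5% of events missed it is already above.

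**Step 4. What f might mean.** If 20 of 1000 attempts failed and 10% of those had an event (both assumed), 20 × 0.10 = 2 events would be lost. The apparent rate would be (26.6 − 2)/1000 = 2.46%. The documents give neither the failed-attempt rate nor the share of events before implant, so f cannot be derived from them.

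**The case against.** The best reply is that implant is shorthand for the implant procedure. Much of the text supports this. The hypothesis line refers to the procedure. All attempts were deliberately put in the analysis population. Follow-up of failed attempts closes at the same point as the endpoint window, and would have little purpose if these subjects could never have an event. The listed exclusions (pericardial drainage, femoral pseudoaneurysm, access-site treatment) suggest that access-phase complications were otherwise thought to be in scope. Text that might settle the matter is redacted (the SAP 2.1 populations, parts of Protocol 14.1.3 and SAP 2.3.1.1) or lies in the CEC Charter, which is not among the documents.

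Much of this stands. A reader might infer that failed attempts have no usable window at all and that the safety rate is biased low. The documents do not support that: the events are collected, one line in 14.1.3 would count them, and redacted text cannot be taken as absent. The pass/fail cut-offs also do not measure the bias, since one event near the limit reverses any threshold test.

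The mismatch remains. Collecting an event is not the same as counting it, and no visible passage reconciles the start of the window with the population. If timing is applied by calendar date, same-day events before implant may count in implanted subjects, but failed attempts still have no implant date.

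**Conclusion.** The inconsistency is real and appears in both documents: the endpoint opens at implant, the population opens at vascular access, and the hypothesis line points to the procedure. The bias is conditional. On the literal reading, any error lowers the rate toward the 2.66% goal; on the procedure reading there is none. Which reading will be applied is not visible.

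The size cannot be established. The figures above rest on an assumed 1000 attempted subjects, a true rate exactly at the goal, and assumed shares of missed events. They show that a small share is enough to push the error rate past its nominal level, not that this will happen. Because this is a hypothesis-tested primary endpoint and the repair is cheap, the wording should be settled before the results are known.

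**What to change.** Use one start point that exists for every attempted subject. Initiation of vascular access is the natural choice, since it already marks prospective enrollment (Protocol 4.5) and the start of safety reporting.

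- Put it in all four endpoint definitions (synopsis, Protocol 4.3.1, Protocol 14.1.3, SAP 1.4.1), in the hypothesis statement and in the CEC instructions.
- Keep the existing end of the window: the later of 7 days after the procedure or hospital discharge.
- State that events in never-implanted subjects count.
- Check the window against the one used with the source of the goal. SAP 2.3.1 takes its goals from a US post-approval study of another device, and the window used there is not visible. If it differs, say so and justify the comparison.

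The cost is a short wording amendment and an aligned adjudication instruction. No new prospective data are needed, because serious events are already reported from vascular access; retrospective events are collected from the date of the implant or attempted implant. The downside for the sponsor is that the observed safety rate may become slightly less favourable.
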